3.4.2. E-Diary Transmission

An e-diary will be considered transmitted if any data for the local reactions, systemic events, or use of antipyretic/analgesic medication are present for any day. If all data are missing for all the items on the e-diary for all 7 days after vaccination, then the e-diary will be considered not transmitted.

3.4.3. Prior/Concomitant Vaccines and Concomitant Medications

The following concomitant medications and vaccinations will be recorded in the CRF:

- All vaccinations received from 28 days prior to study enrollment until the 1-month follow-up visit (Visit 3, primary study/Visit 6, booster study).
- Prohibited vaccines and medications listed in the protocol, Section 6.5.1, will be recorded, to include start and stop dates, name of the medication, dose, unit, route, and frequency.

Prior and concomitant vaccines and concomitant medications will be coded using the WHO Drug Dictionary.

3.5. Safety Endpoints

Local reactions, systemic events, AEs, and SAEs have been described above ([Section 3.1.4](#)) in the Primary Safety Endpoints section.

4. ANALYSIS SETS (POPULATIONS FOR ANALYSIS)

Analysis populations are defined for the statistical analysis of safety and immunogenicity results in the table below. For the specified criteria in each population definition that are not associated with unblinded information (randomized or actual vaccine received), data for all participants will be assessed to determine if participants meet the criteria for inclusion in each analysis population prior to unblinding and releasing the database for analysis, and the classifications will be documented per standard operating procedures.

Primary Study

Population	Description
Enrolled	All participants who sign the ICD.
Randomized	All participants who are assigned a randomization number in the IRT system.
Evaluable immunogenicity	All participants who 
 1. are eligible and randomized; 2. receive 2 doses of vaccine to which they are randomized, with Dose 2 received within the predefined window (19-42 days, inclusive, after Dose 1); 3. have at least 1 valid immunogenicity result within an appropriate window 1 month after Dose 2 (28-42 days, inclusive, after Dose 2); 4. negative for both SARS-CoV-2 tests (RT-PCR and N-binding antibody assay) at both the Day 1 and 1-month post-Dose 2 visits; and 5. have no other important protocol deviations as determined by the clinician.
All-available immunogenicity	All randomized participants who receive at least 1 dose of the study intervention with at least 1 valid and determinate immunogenicity result after vaccination.
Safety	All randomized participants who receive at least 1 dose of the study intervention.

Booster Study

Population	Description
Enrolled	All participants who sign the ICD at Visit 4.
Randomized	All participants who are assigned a randomization number at Visit 4 in the IRT system.
Booster evaluable immunogenicity	All participants who 
 1. are eligible and randomized; 2. receive 2 doses of vaccine to which they are randomized in the primary study with Dose 2 received within the predefined window (19-42 days, inclusive, after Dose 1) and receive Dose 3 to which they are randomized in the booster study with Dose 3 received with the predefined window (83 to 97 days, inclusive, after Dose 2); 3. have at least 1 valid immunogenicity result within an appropriate window 1 month after Dose 3 (28-42 days, inclusive, after Dose 3); 4. are negative for both SARS-CoV-2 tests (RT-PCR and N-binding antibody assay) at the Day 1 (Dose 1), 1-month post-Dose 2, Dose 3, and 1-month post-Dose 3 visits; and 5. have no other important protocol deviations as determined by the clinician.
Booster all-available immunogenicity	All randomized participants who receive Dose 3 of the study intervention with at least 1 valid and determinate immunogenicity result after Dose 3.
Safety	All randomized participants who receive Dose 3 of the study intervention.

The important protocol deviations for both the primary study and booster study will be determined by the medical monitor. An important protocol deviation is a protocol deviation that, in the opinion of Pfizer's clinician, would materially affect assessment of immunogenicity, eg, participant receipt of a prohibited vaccine or medication that might affect immune response or a medication error with suspected decrease in potency of the vaccine. Pfizer's clinician will identify those participants with important protocol deviations that result in exclusion from analysis populations before any unblinded analysis.

In the primary study, for all the immunogenicity endpoints, the analysis will be based on the evaluable immunogenicity population. An additional analysis will be performed based on the all-available immunogenicity population if there is over 10% difference in sample size between the all-available immunogenicity population and the evaluable immunogenicity population. Participants will be summarized according to the vaccine group to which they were randomized. The booster study will be assessed similarly.

The safety analyses in the primary study and the booster study will be based on the respective safety population. Participants will be summarized by vaccine group according to the study interventions they actually received.

5. GENERAL METHODOLOGY AND CONVENTIONS

Methodology for summary and statistical analyses of the data collected in this study is described here. The SAP may modify what is outlined in the protocol where appropriate; however, any major modifications of the primary endpoint definitions or their analyses will also be reflected in a protocol amendment.

The majority of Pfizer staff will be blinded to study intervention allocation. The blinded study team will become unblinded to the primary study randomization information at the time of the database release of the primary study. These same study team members will remain blinded to the randomization information for the booster study until completion of that phase.

All laboratory testing personnel performing serology assays will remain blinded to study intervention assigned/received throughout the testing for the primary study and for the booster study, respectively. Further details can be found in the protocol, Section 6.3. The timing for statistical analysis is specified in [Section 7](#).

5.1. Hypotheses and Decision Rules

5.1.1. Immunogenicity Hypotheses

Primary Study

There are 2 primary immunogenicity objectives on manufacturing lot comparisons. Hypothesis testing will be used to assess the first primary immunogenicity objective, the similarity of the immune response induced by BNT162b2 across the 3 US lots. The null hypothesis (H_{01}) is

$$H_{01}: |\ln(\mu_1)-\ln(\mu_2)| \geq \ln(1.5) \text{ or } |\ln(\mu_1)-\ln(\mu_3)| \geq \ln(1.5) \text{ or } |\ln(\mu_2)-\ln(\mu_3)| \geq \ln(1.5)$$

where $\ln(1.5)$ corresponds to a 1.5-fold equivalence margin, and $\ln(\mu_1)$, $\ln(\mu_2)$, and $\ln(\mu_3)$ are the natural log of the geometric mean of full-length S-binding IgG levels measured 1 month after Dose 2 from participants receiving BNT162b2 30 μg from the US lots in Arm 1, Arm 2, and Arm 3, respectively.

Two lots will be considered similar if the 2-sided 95% CI for the GMR is contained in the interval (0.67, 1.5). The 3 lots will be considered similar if the 1.5-fold equivalence criterion is met for all 3 between-lot comparisons (Arm 1 to Arm 2, Arm 1 to Arm 3, and Arm 2 to Arm 3).

Hypothesis testing will be used to assess the second primary immunogenicity objective, the similarity of the immune response induced by BNT162b2 30 μg in the EU lot to that in the US lots. The null hypothesis (H_{02}) is

$$H_{02}: |\ln(\mu_4)-\ln(\mu_p)| \geq \ln(1.5)$$

where $\ln(1.5)$ corresponds to a 1.5-fold equivalence margin, and $\ln(\mu_4)$ and $\ln(\mu_p)$ are the natural log of the geometric mean of full-length S-binding IgG levels measured 1 month after Dose 2 from participants receiving the BNT162b2 30 μg from the EU lot and the 3 pooled US lots, respectively.

The EU lot and the US lots will be considered similar if the 2-sided 95% CI for the GMR is contained in the interval (0.67, 1.5).

The primary immunogenicity objective on dose comparison is to assess the noninferiority of the immune response of the 20- μg dose to the standard 30- μg dose (prepared from the same lot). The null hypothesis is

$$H_{03}: \ln(\mu_{20})-\ln(\mu_{30}) \leq \ln(0.67)$$

where $\ln(0.67)$ corresponds to a 1.5-fold noninferiority margin and $\ln(\mu_{20})$ and $\ln(\mu_{30})$ are the natural log of the geometric mean of the SARS-CoV-2 neutralizing titers measured 1 month after Dose 2 from participants receiving the BNT162b2 20- μg dose or 30- μg dose (from the same US lot), respectively.

Noninferiority of the 20- μ g dose to the corresponding 30- μ g dose will be declared if the lower limit of the 2-sided 95% CI for the GMR is >0.67 .

Booster Study

Not applicable.

CCI [REDACTED]
[REDACTED]

[REDACTED]

[REDACTED]

[REDACTED]

CCI [REDACTED]

[REDACTED]

5.2. General Methods

Unless stated otherwise, “vaccine group” in this document refers to participants receiving any 1 of the three 30- μ g US lots, the (30- μ g) EU lot, or the 20- μ g dose group in the primary study and to participants receiving BNT162b2 at 30 μ g or BNT162b2.B.1.351 at 30 μ g in the booster study. CIs for all endpoints in the statistical analysis will be presented as 2-sided at the 95% level unless specified otherwise.

5.2.1. Analyses for Binary Data

Descriptive statistics for categorical variables (eg, proportions) are the percentage (%), the numerator (n) and the denominator (N) used in the percentage calculation, and the 95% CI where applicable.

The exact 95% CI for binary endpoints for each group will be computed using the F distribution (Clopper-Pearson).¹

[REDACTED]

[REDACTED]

5.2.2. Analyses for Continuous Data

Unless otherwise stated, descriptive statistics for continuous variables are n, mean, median, standard deviation, minimum, and maximum.

Continuous immunogenicity outcomes of titers or IgG concentrations will be performed on the natural log scale, and the results will be exponentiated and reported in the original scale.

5.2.2.1. Geometric Mean Ratios

Model-Based

As the primary approach in the primary study, the GMR and associated 95% CI will be calculated by exponentiating the difference in LS means and the corresponding CIs based on analysis of logarithmically transformed assay results using a linear regression model.

Unadjusted

The GMRs in the primary study will be calculated as the mean of the difference of logarithmically transformed assay results between 2 vaccine groups and exponentiating the mean. Two-sided CIs will be obtained by calculating CIs using Student's t-distribution for the mean difference of the logarithmically transformed assay results and exponentiating the confidence limits.

5.2.2.2. Geometric Means

The geometric means will be calculated as the mean of the assay results after making the logarithm transformation and then exponentiating the mean to express results on the original scale. Two-sided 95% CIs will be obtained by taking log transforms of assay results, calculating the 95% CI with reference to Student's t-distribution, and then exponentiating the confidence limits.

5.2.2.3. Geometric Mean Fold Rises

GMFRs are defined as ratios of the results at a later time point to the results at an earlier time point. GMFRs are limited to participants with nonmissing values at both time points.

GMFRs will be calculated as the mean of the difference of logarithmically transformed assay results (later time point minus earlier time point) and exponentiating the mean. The associated 2-sided 95% CIs will be obtained by constructing CIs using Student's t-distribution for the mean difference on the logarithm scale and exponentiating the confidence limits.

5.2.2.4. Reverse Cumulative Distribution Curves

Empirical RCDCs will plot proportions of participants with values equal to or exceeding a specified assay value versus the indicated assay value, for all observed assay values. Data points will be joined by a step function with data points on the right side of the step.

5.2.2.5. Antibody Response Curves

In the booster study, antibody response will be graphed for full-length S-binding IgG concentrations and SARS-CoV-2 neutralizing titers by vaccine group at baseline (before Dose 1) and at postvaccination blood sampling time points. The curves will display the geometric mean and 95% CI at each of the time points with a line connecting the geometric means for each vaccine group across time.

5.3. Methods to Manage Missing Data

A partial AE start date (missing day or missing both month and day) will be imputed by assigning the earliest possible start date using all available information, such as the stop date of the AE and the vaccination date(s) from the same participant, following the Pfizer standard for handling incomplete AE start date. A complete missing start date for an AE is not allowed in the data collection.

The LLOQ for each assay will be provided by Vaccine Research & Development as part of the electronic data transfer or within the Clinical Testing Completion Memo prior to statistical analysis. Assay results above the LLOQ will be reported, and values below the LLOQ, denoted as BLQ, will be imputed as $0.5 \times \text{LLOQ}$ for analysis.

No additional imputation will be applied to other missing data.

6. ANALYSES AND SUMMARIES

6.1. Primary Endpoints

6.1.1. Primary Immunogenicity Endpoints

6.1.1.1. Primary Study – Full-Length S-Binding IgG Concentrations at 1 Month After Dose 2 for Participants Receiving Vaccine From the US Lots

6.1.1.1.1. Main Analysis

- Estimands: GMR from one US lot to another lot (Arm 1/Arm 2, Arm 1/Arm 3, and Arm 2/Arm 3) ([Section 2.1](#)).
- Analysis set: Evaluable immunogenicity population, all-available immunogenicity population (as applicable) ([Section 4](#)).
- Analysis time point: 1 Month after Dose 2.
- Analysis methodology: The GMRs and corresponding 95% CIs will be calculated using the linear regression model with terms of age and vaccine group as described in [Section 5.2.2.1](#). The similarity will be assessed by comparing the limits of the 95% CI against the equivalence margins ([Section 5.1.1](#)).
- Intercurrent events and missing data: Serology data deemed unevaluable because of noncompliance with the key protocol criteria will be excluded. Missing data will not be imputed.

- Reporting results: The LS GMC and the corresponding 95% CI for IgG concentrations will be presented for each US lot. The model-based estimate of GMR for each pair of lots being compared (Arm 1/Arm 2, Arm 1/Arm 3, and Arm 2/Arm 3) and the corresponding 95% CI will be calculated.

Figures:

A forest plot of GMRs with 95% CIs for each pair of lots being compared will be presented.

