### **Prior/Concomitant Therapy:**

- 8. Primary study: Previous vaccination with any coronavirus vaccine.
  - Booster study: Previous vaccination with any coronavirus vaccine outside of this study.
- 9. Receipt of medications intended to prevent COVID-19.
- 10. Individuals who receive treatment with radiotherapy or immunosuppressive therapy, including cytotoxic agents or systemic corticosteroids (if systemic corticosteroids are administered for ≥14 days at a dose of ≥20 mg/day of prednisone or equivalent), eg, for cancer or an autoimmune disease, or planned receipt throughout the study. Inhaled/nebulized, intra-articular, intrabursal, or topical (skin or eyes) corticosteroids are permitted.
- 11. Receipt of blood/plasma products or immunoglobulin, from 60 days before study intervention administration or planned receipt throughout the study.

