#### 9.4.2. Primary Endpoint(s)

#### **Primary Study**

Endpoint	Statistical Analysis Methods	
Immunogenicity	GMRs of full-length S-binding IgG levels between the US lots	
	For full-length S-binding levels, the GMRs for each between-lot comparison (Arm 1/Arm 2, Arm 1/Arm 3, and Arm 2/Arm 3) at 1 month after Dose 2 will be provided along with associated 2-sided 95% CIs (see Section 9.4.1.2.1).	
	Using a 1.5-fold equivalence margin, 2 lots will be considered similar if the 2-sided 95% CI for each GMR is contained in the interval (0.67, 1.5).	
	GMR of full-length S-binding IgG levels between the EU lot and the 3 US lots	
	The GMR of the EU lot (Arm 4) to the pooled US lots (Arm 4/pooled Arms 1, 2, and 3) at 1 month after Dose 2 will be provided along with associated 2-sided 95% CIs (see Section 9.4.1.2.1).	
	Using a 1.5-fold equivalence margin, the EU lot Arm 4) and the pooled US lots (Arms 1-3) will be considered similar if the 2-sided 95% CI for the GMR is contained in the interval (0.67, 1.5).	

Endpoint Statistical Analysis Methods	
	GMR of SARS-CoV-2 neutralizing titers between the 20-μg dose and the corresponding 30-μg dose
	The GMR of the 20- $\mu$ g dose (Arm 5) to the corresponding 30- $\mu$ g dose (Arm 1, 2, or 3) (20 $\mu$ g/30 $\mu$ g) at 1 month after Dose 2 will be provided along with associated 2-sided 95% CIs (see Section 9.4.1.2.1).
	Using a 1.5-fold noninferiority margin, noninferiority of the 20-µg dose (Arm 5) to the corresponding 30-µg dose (Arm 1, 2, or 3) will be declared if the lower limit of the 2-sided 95% CI for the GMR is >0.67.
	As the primary approach for these similarity and noninferiority assessments, a linear regression model that includes a term for age and vaccine group will be used to calculate the adjusted GMR and 2-sided 95% CI. The unadjusted GMR and CI will also be calculated.
Safety	Descriptive statistics will be provided for each reactogenicity endpoint for each dose and vaccine group. Local reactions and systemic events from Day 1 through Day 7 after each vaccination will be presented by severity and cumulatively across severity levels. Descriptive summary statistics will include counts and percentages of participants with the indicated endpoint and the associated Clopper-Pearson 95% CIs (see Section 9.4.1.1).

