3. ENDPOINTS AND BASELINE VARIABLES: DEFINITIONS AND CONVENTIONS

3.1. Primary Endpoints

3.1.1. Primary Study – Primary Immunogenicity Endpoints – Lot Comparisons

- Full-length S-binding IgG levels at 1 month after Dose 2 for participants receiving vaccine from the US lots (Arms 1, 2, and 3)
- Full-length S-binding IgG levels at 1 month after Dose 2 for participants receiving vaccine from the EU lot (Arm 4) and the 3 pooled US lots (pooled Arms 1, 2, and 3)

Concentrations of IgG levels will be determined in all participants at Visit 1 (Day 1) and Visit 3 (1 month after Dose 2) using the SARS-CoV-2 full-length S-binding IgG-level assay.

Values below the LLOQ will be set to $0.5 \times \text{LLOQ}$ for the analysis. The LLOQ value for full-length S-binding IgG will be included in the analysis specification once it is available.

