3.1.2. Primary Study – Primary Immunogenicity Endpoint – Dose Comparison

- SARS-CoV-2 neutralizing titers at 1 month after Dose 2 for participants receiving 30- μg or 20- μg doses (prepared from the same manufacturing lot)

Titers will be determined in all participants at Visit 1 (Day 1) and Visit 3 (1 month after Dose 2) using the SARS-CoV-2 neutralizing assay.

Values below the LLOQ will be set to $0.5 \times \text{LLOQ}$ for the analysis. The LLOQ value for neutralizing titers will be included in the analysis specification once it is available.

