6.2. Secondary Endpoints

6.2.1. Immunogenicity Endpoints

6.2.1.1. Full-Length S-Binding IgG Levels

6.2.1.1.1. Main Analysis

- Estimands: GMCs ([Section 2.1](#)).
- Analysis set: Evaluable immunogenicity population, all-available immunogenicity population (as applicable) ([Section 4](#)).
- Analysis time points: Baseline (before Dose 1) and 1 month after Dose 2.
- Analysis methodology: Descriptive statistics.
- Intercurrent events and missing data: Serology data deemed unevaluable because of noncompliance with the key protocol criteria will be excluded. Missing data will not be imputed.
- Reporting results: The GMC and corresponding 2-sided 95% CIs for baseline and 1 month after Dose 2 will be presented for each vaccine group, as well as for the pooled US lots.

Figures:

Empirical RCDCs will be presented for the IgG concentrations for each vaccine group and the pooled US lots. There will be 2 figures, 1 for the 3 US lots and 1 for the pooled US lots, and the EU lot. Each figure will display 6 or 4 curves respectively, one for baseline (Day 1) and one for 1 month after Dose 2, for each of the vaccine groups or the pooled US lots. Only the evaluable immunogenicity population will be used.

6.2.1.2. Fold Rises in Full-Length S-Binding IgG Levels From Baseline to 1 Month After Dose 2

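### The three primary GMR models leave out the Visit 1 result of the endpoint assay: a small efficiency loss in the evaluable set, probably larger in the all-available set

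*SAP*

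**What the plan says.** SAP 6.1.1.1.1 (US lots), 6.1.1.2.1 (EU lot against pooled US lots) and 6.1.1.3.1 (20 µg against 30 µg) give one model: the GMR is "calculated using the linear regression model with terms of age and vaccine group". Protocol 9.4.2 agrees: "a linear regression model that includes a term for age and vaccine group will be used to calculate the adjusted GMR". The only sensitivity analysis (SAP 6.1.1.1.2, 6.1.1.2.2, 6.1.1.3.2) repeats the comparison with an unadjusted GMR.

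The endpoint assays are also run before Dose 1. For IgG, SAP 3.1.1 says: "Concentrations of IgG levels will be determined in all participants at Visit 1 (Day 1) and Visit 3". For neutralization, SAP 3.1.2 says: "Titers will be determined in all participants at Visit 1 (Day 1) and Visit 3". These baselines are used only descriptively. SAP 6.2.1.1.1 states: "The GMC and corresponding 2-sided 95% CIs for baseline and 1 month after Dose 2 will be presented for each vaccine group", and fold rises, distribution curves and subgroup summaries follow the same pattern. No planned comparison between groups conditions on them.

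The evaluable set in SAP section 4 must be "negative for both SARS-CoV-2 tests (RT-PCR and N-binding antibody assay) at both the Day 1 and 1-month post-Dose 2 visits". Protocol 5.2 excludes diagnosed COVID-19 (criterion 4), and criterion 8 reads "Primary study: Previous vaccination with any coronavirus vaccine". SAP 5.3 sets results below LLOQ to half the LLOQ. The age and group model is also named for the all-available set, which has no baseline-negativity criterion. That set is analyzed if its size differs from the evaluable set by more than 10%.

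**The concern.** A pre-dose measurement of the outcome is a natural covariate in a randomized comparison, and here it is already collected. If some participants have measurable antibody at Visit 1 and respond more strongly, their extra response sits in the residual error and the CIs used for the similarity and noninferiority decisions are wider than they need be.

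The evaluable set narrows this possibility without closing it. Its infection criteria use RT-PCR and N-binding antibody, which are not the endpoint assays, and nothing requires baseline S-binding IgG or neutralizing titer to be below LLOQ. Criterion 4 covers diagnosed disease only, so an undiagnosed earlier infection can be enrolled, and Protocol 8.1 makes dosing independent of the test results. The all-available set has no such screen.

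**Working it through.** **Inputs from the documents.** EU comparison: 135 against 810 evaluable, stated power 92.8%, similarity interval (0.67, 1.5), 2-sided 95% CI (Protocol 9.1.2, 9.2). US lots and dose comparison: 270 per group, stated powers 91.7% and 94.7%. Nonevaluable rate: 20%. The SD and the assumed true difference are redacted.

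**Assumptions.** The share *s* with detectable baseline antibody, and the factor *F* by which their later response is higher. The documents give neither.

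**Step 1: tie to the plan's figure.** The 92.8% cannot be reproduced independently without the SD, so I solved for the SD that gives it at no true difference.
- SE = SD × √(1/135 + 1/810) = SD × 0.09296
- Power = Φ(ln 1.5/SE − 1.96) + Φ(−ln 0.67/SE − 1.96) − 1
- SD = 1.153 gives SE = 0.1072 and power = Φ(1.82) + Φ(1.78) − 1 = 92.8%

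A true between-lot difference would imply a smaller SD: about 0.98 at 1.1-fold and 0.70 at 1.2-fold.

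**Step 2: precision gain in the evaluable set.** With total SD held at 1.153, the share of variance explained is r² = s(1 − s)(ln F)²/SD², and the SE is multiplied by √(1 − r²).

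| s, F | r² | SE ratio, formula | SE ratio, simulated | EU power |
|---|---|---|---|---|
| all below LLOQ | 0 | 1 | 1 | 92.8% |
| 1%, 3-fold | 0.01 × 0.99 × 1.207/1.329 = 0.009 | 0.995 | 0.997 | 93.0-93.1% |
| 5%, 4-fold | 0.05 × 0.95 × 1.922/1.329 = 0.069 | 0.965 | 0.970 | 94.4-94.7% |

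The SE therefore falls by 0.3-0.5% in the second row and 3.0-3.5% in the third. A smaller SD raises r² for the same *s* and *F*. With a milder assumption (0-2% detectable, 2-fold) and SD between 0.6 and 1.3, CI half-widths narrow by 0-1.3%.

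For the other two comparisons, a baseline correlation of 0.1 to 0.2 would raise power from 91.7% to 92.0-93.0% (US lots, 1.1-fold true difference) and from 94.7% to 94.9-95.5% (dose, true GMR 1.0).

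**Step 3: chance imbalance.** The two-SE effect of an uneven share of detectable baselines on the EU GMR is exp(2 × √(s(1 − s)) × ln F × 0.09296).
- 1%, 3-fold: about 1.02
- 5%, 4-fold: exp(2 × 0.2179 × 1.386 × 0.09296) = 1.06

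Total two-SE variation is exp(2 × 0.1072) = 1.24. The imbalance is one part of that, and the CI already includes it.

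**Step 4: all-available set.** At an illustrative SD of 0.9 and a 5-fold effect, 10% detectable gives r² = 0.09 × 2.590/0.81 = 0.29 (CI 16% narrower), and 20% gives 0.16 × 2.590/0.81 = 0.51 (30% narrower). At SD 1.3 the narrowing is 7% and 13%.

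The planned 20% nonevaluable rate makes the 10% trigger plausible. It is not certain, because participants without a valid postvaccination result leave both sets.

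**The case against.** The strongest reply is that age-only adjustment is a legitimate prespecified choice and that the primary set leaves little to adjust for. Day 1 negativity on two tests, the exclusions for diagnosed COVID-19 and prior vaccination, and one constant for results below LLOQ should make baseline nearly constant. Nothing in the documents suggests that the remaining detectable group is material. This stands, and it is why the gain in the evaluable set is called small and possibly nil.

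A reader might infer that leaving out baseline biases the lot or dose GMRs, or that chance imbalance makes the tests unsafe. The documents do not support that: assignment is randomized and the CI covers chance imbalance. Nor can it be said that every CI is wider than necessary, since this depends on some baselines being detectable. Any extra width makes similarity and noninferiority harder to declare, so the plan errs on the conservative side.

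Three further replies stand in part:
- Baseline summaries by arm will show an imbalance, but they do not adjust for it.
- The all-available analysis is additional and conditional. It also readmits participants infected during the study, and a Visit 1 covariate cannot account for infection after Visit 1.
- A linear term alone would be fragile when most baselines equal one constant, because a few detectable values would set the slope. The remedy has to deal with this.

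**Conclusion.** The point holds as one of efficiency and robustness. Under the assumed 1-5% detectable share and 3- to 4-fold response, adjustment in the evaluable set would lower the SE by about 0.3-3.5% and raise EU power from 92.8% to about 93-95%. With all baselines below LLOQ it would change nothing. These figures rest on *s*, *F* and an SD solved at no true difference, none of which the documents state.

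The case is stronger for the all-available analysis. It uses the same model without a baseline-negativity criterion and may well be triggered, although its gain also depends on assumed inputs. The change is worth making because the data are already collected and the loss is negligible if baseline proves uninformative.

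**What to change.** Before unblinding, in SAP 6.1.1.1.1, 6.1.1.2.1 and 6.1.1.3.1:
- Add two terms to age and vaccine group: the ln Visit 1 result of the same assay (below LLOQ set by the SAP 5.3 rule), and an indicator for baseline at or above LLOQ. The indicator keeps a few detectable values from setting the slope alone.
- Use this model for both the evaluable and the all-available analyses, and drop the two terms if every baseline is below LLOQ.
- State how a missing Visit 1 result is handled. SAP 5.3 allows no further imputation, so these participants would otherwise leave the adjusted model.
- Keep the unadjusted GMR as the sensitivity analysis, and report the share with baseline at or above LLOQ by arm.

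The cost is two model terms and no new data. Protocol 9.4.2 should be changed to match, and the sponsor must judge whether this counts as a major modification needing a protocol amendment under Protocol section 9 and SAP section 5.

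If the primary model is left as it is, prespecify the baseline-adjusted GMR as a sensitivity analysis and use it for the all-available set.
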